# Data Analysis

FLACC, heart rate, and oxygen saturation will be measured at 10 distinct time points (Table 1) during serial casting and following in-office TAL. Changes in FLACC score, heart rate, and oxygen saturation will be compared between treatment and control cohorts utilizing a two-way ANOVA with a Geisser-Greenhouse correction for matched time measures. A Sidak's multiple comparisons test will be utilized to assess differences between cohorts at each of the 10 time points assessed. To compare number of

complications between cohorts, data will be collected at 3-weeks post TAL and analyzed using a non-parametric Mann-Whitney test, given the ordinal nature of the data. Similar non-parametric analysis with correction for multiple comparisons between cohorts will be utilized to assess changes in responses to REDCap surveys. Statistical analysis will be conducted utilizing GraphPad Prism 8.3.0. Statistical significance will be p<0.05.

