# 6.0 Study Procedures

# Weekly Casting Visits

Once study consent is obtained, the subject will undergo serial casting weekly by one of two board-certified Pediatric Orthopaedic surgeons using the Ponseti method to address their congenital idiopathic clubfoot. CCLS will be present to provide coping support and standardize the environment. This is routine care at our institution. During these castings, patient will wear pulse ox on hand, with mitten covering tool if needed, in order to measure heart rate and oxygen saturation. The CCLS, with assistance from a trained research assistant, will assess the subject's pain and temperament utilizing observational data and data collected from FLACC Scale. Observational assessment is also routine care, but the FLACC data, pulse ox and temperament questionnaire are new, being collected strictly for the study. Primary data will be obtained during casting of first foot and, in the case of bilateral clubfoot patients, a subgroup will be created utilizing data collected during casting of both feet.

Data collection during weekly castings will be obtained by a trained research assistant and will be event based, utilizing pulse ox and FLACC scale. Time points are as follows:

- Baseline before cast placement (patient placed on treatment table)
- Start of casting, after cast padding placed (1st cast if bilateral)
- End of casting (2nd cast if bilateral)

If the subject does not require tenotomy after the weekly casting, they will be withdrawn from the study.

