# Tenotomy

On the day of the subject's tenotomy they will receive pain control based on their group assignment- L.M.X.4 cream (with J-Tip Saline) or J-Tip with 0.25mL of 1% Xylocaine MPF (with placebo cream). The treating physician will provide a Dimeglio score. The following procedures will take place:

- Baseline: FLACC and pulse ox data will be recorded as baby is positioned on treatment table
- Application of randomized topical cream (either L.M.X.4 or placebo cream) for 30 minutes timed.
- Peak FLACC and pulse ox data will be recorded within 5 seconds of application of LMX 4 or Placebo Cream
- Consent for tenotomy procedure will be obtained (routine care).
- Baseline #2: FLACC and pulse ox data will be recorded 30 minutes after cream application
- Parents will leave room (routine care).
- Patient stays with healthcare staff (Physician, nurse, CCLS, cast tech, trained research assistant)
- Cream will be removed from the subject's foot (routine care). Peak FLACC and Pulse Ox will be recorded within 5 seconds after cream removal.
- Baseline #3: FLACC and pulse ox data will be recorded 30 seconds after cream removal
- J-Tip injection with 1% Xylocaine MPF or saline. Peak FLACC scale measurements and pulse ox measurements will be recorded within 5 seconds of injection (1st foot if bilateral)
- Following J-Tip injection there will be a 3-minute break, baby will be calmed during this time.
- Baseline #4: FLACC scale measurements and pulse ox measurements 3 minutes after J-Tip injection
- Tenotomy will be performed
  - FLACC Scale data and Pulse Ox data will be measured during the following events:
    - Percutaneous incision for TAL (1st foot if bilateral)- Peak FLACC scale and Pulse Ox data will be recorded within 5 seconds of poke of scalpel
    - Start of casting, after cast padding placed (1st cast if bilateral)

• End of casting (2nd cast if bilateral)

Adverse local effects of the cream and/or J-Tip injection will be noted (skin redness, swelling, rash, etc). Procedural complications will be recorded (excessive bleeding, concern for neurovascular injury, etc).

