# 10.0 Statistical Considerations

# **Power Analysis**

A power analysis was conducted to determine the sample size needed to find a clinically meaningful difference of 2.5 point in the FLACC score (SD=3) between the two methods. With alpha=0.05, power=0.8, and and effect size d=.83, at least 24 patients per group are required (N=48). Assuming a 20% participant lost to follow-up rate, we will need to enroll 29 patients per group (N=58).

An interim power analysis was conducted to determine the sample size to find a clinically meaningful difference of 2.0 points in the FLACC score between the two methods. This was performed using the maximum SD of the FLACC score observations of the first 39 patients (SD=4.13). With alpha=0.05 and power=0.8, at least 47 patients per group are required (N=94).

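### The ten analysed time points in Section 10 do not match the Section 6 schedule, and the ten-test Sidak family takes in at least one pre-treatment reading and cuts power at the incision

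*Combined protocol and SAP*

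**What the plan says.** Section 10.0, Data Analysis, states that FLACC, heart rate and oxygen saturation are "measured at 10 distinct time points (Table 1) during serial casting and following in-office TAL". The arms are compared by a two-way ANOVA with matched time measures, and then: "A Sidak's multiple comparisons test will be utilized to assess differences between cohorts at each of the 10 time points assessed". The threshold is given as "Statistical significance will be p<0.05". No time point is named as the main one.

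Section 6.0 has two separate measurement lists. Under Weekly Casting Visits, "Data collection during weekly castings will be obtained by a trained research assistant and will be event based", with three readings per visit. Under Tenotomy there is a longer list that opens with "Baseline: FLACC and pulse ox data will be recorded as baby is positioned on treatment table" and runs to the end of casting. Section 5.0 (Randomization) places allocation on or after the final casting visit, and the study products are given only on tenotomy day.

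Section 10.0, Power Analysis, sizes the trial for a "clinically meaningful difference of 2.0 points in the FLACC score between the two methods", and concludes: "With alpha=0.05 and power=0.8, at least 47 patients per group are required (N=94)". It mentions no adjustment for multiple time points.

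**The concern.** The sentence in Section 10 that defines the analysed readings fits neither list in Section 6. An analyst could assemble different sets of readings from the same text, and would have to choose after data exist.

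The choice matters in two ways. First, a reading taken before any study product cannot differ between arms because of treatment. Including it in the between-arm tests uses part of the Sidak allowance for nothing and adds a null reading to the ANOVA treatment effect. Second, Aim 1 asks which method gives more pain relief to infants undergoing the tenotomy. The incision reading bears on that most directly, yet it has the same standing as nine others and is tested at about a tenth of the alpha assumed in the sample size.

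**Working it through.** **Counting the readings (Section 6.0, Tenotomy).**

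| No. | Reading | Position |
|---|---|---|
| 1 | First baseline | before any study product |
| 2 | Cream application, within 5 seconds | before incision |
| 3 | Baseline #2, 30 minutes after cream | before incision |
| 4 | Cream removal | before incision |
| 5 | Baseline #3 | before incision |
| 6 | J-Tip injection | before incision |
| 7 | Baseline #4 | before incision |
| 8 | Incision | at incision |
| 9 | Start of casting | after incision |
| 10 | End of casting | after incision |

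That is 7 + 1 + 2 = 10, none of them in serial casting. Taking Section 10's wording literally, with one casting visit, gives 3 casting readings + 3 from the incision onward = 6. Both full lists give 3 + 10 = 13. Only the tenotomy-day list gives ten.

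**The plan's own sample sizes.** Two-sample t-test, two-sided alpha 0.05, power 0.80. Sidedness is not stated, so two-sided is assumed.
- Initial calculation: d = 2.5/3 = 0.83 gives 23.6, so 24 per group. The plan's 24 reproduces with no multiplicity adjustment.
- Interim calculation: d = 2.0/4.13 = 0.484 gives 67.9, so 68 per group. The plan's 47 does not reproduce. This is a separate problem, but it sets the starting point for power below.

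**Sidak level per test:** 1 − 0.95^(1/k).
- k = 10: 0.0051
- k = 4: 0.0127
- k = 3: 0.0170
- k = 1: 0.05

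**Power for a 2.0-point difference at one reading, 47 per arm, two-sided t-test.**

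| Tests in family | Level per test | SD 4.13 | SD 3 |
|---|---|---|---|
| 10 | 0.0051 | 31% | 64% |
| 4 | 0.0127 | 43% | 75% |
| 3 | 0.0170 | 47% | 79% |
| 1 | 0.05 | 64% | 89% |

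SD 4.13 is the maximum SD seen in the first 39 patients, and SD 3 is the plan's initial assumption. Neither is stated to be the SD at the incision, so both are shown. At SD 4.13, 80% power needs 116 per group with ten tests and 68 with one.

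**Sensitivity.**
- One-sided tests at SD 4.13 and 47 per arm: 40% with ten tests, 75% with one.
- Section 5.0 asks for 94 patients at each site and names two sites. If that means 94 per arm overall, power at SD 4.13 is 69% with ten tests and 91% with one.

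The loss from the ten-test family is present in every case.

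**The case against.** The exact match of ten with ten suggests that Table 1 simply lists the tenotomy-day readings. If so, the phrase about serial casting is loose wording and no casting-visit reading enters the ANOVA. That stands as a likely explanation, but the first baseline is still among the ten and the power loss is unchanged.

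A reader might infer that no treatment effect can exist at any of the seven pre-incision readings. The documents do not support this. By cream removal one arm has had 30 minutes of active cream and the other placebo. At the J-Tip injection the injected content differs too, and Baseline #4 follows three minutes later. The arms can differ at all three. Section 3.0 itself summarises earlier trials that recorded pain at anaesthetic application. What is certain is narrower: none of the seven can show incision pain, and only the first baseline, plus any casting-visit readings, precedes treatment.

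A reader might also infer that the ANOVA treatment effect shrinks to 3/10 × 2.0 = 0.6 points. That assumes a zero effect at all seven earlier readings, which does not follow, and it ignores that averaging ten readings also changes the SD.

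Nor is the whole shortfall from 80% due to the time points. At SD 4.13, one unadjusted test already has only 64%, because 47 per group does not follow from its stated inputs. Finally, Sidak controls familywise error, so there is no false-positive concern.

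**Conclusion.** Section 10's description of the analysed readings contradicts Section 6 and must be reconciled with it. That the ten are the tenotomy-day readings is an inference from the count, not something the available text settles.

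On that inference, at least one of the ten between-arm tests is at a reading where treatment can have no effect, and the incision is tested at 0.0051 although the sample size used 0.05. With 47 per arm and a 2.0-point difference, this takes power at the incision from 64% to 31% at SD 4.13, a loss of 33 percentage points, or from 89% to 64% at SD 3, a loss of 25. These figures assume two-sided t-tests and no dropout. They describe lost power and an undefined main result, not inflated error. The further gap from 64% to 80% at SD 4.13 belongs to the sample-size calculation.

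**What to change.** Amend Section 10.0, Data Analysis, to:

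1. State that the analysed readings are those of tenotomy day, list them, and align the text with Table 1 and both Section 6 lists.
2. Name FLACC at the incision (first foot if bilateral) as the single main between-arm test, at alpha 0.05, and state whether it is two-sided.
3. Take the first tenotomy-day baseline and the casting-visit FLACC out of the between-arm tests and use them as covariates. Prespecify one casting-visit summary, since the number of visits will vary, and confirm that the named software can fit the adjusted model.
4. Keep the J-Tip injection peak, start of cast and end of cast as a secondary family of three under Sidak (0.0170 each), labelled as secondary to the main test. Keeping the injection peak matters because active cream could benefit the control arm there.
5. Report the other readings descriptively.

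The cost is wording only, with no new data. The small downside is that cream application, cream removal and the later baselines are described rather than tested. The change should be made before any unblinded comparison. It does not repair the sample size, which needs its own correction.

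### Per-time-point comparisons between arms make no use of the pre-cream reading; they are valid, but give up precision of unknown and possibly negligible size

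*Combined protocol and SAP*

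**What the plan says.** Section 10.0, Data Analysis, is the only analysis text for FLACC, heart rate and oxygen saturation. It says: "Changes in FLACC score, heart rate, and oxygen saturation will be compared between treatment and control cohorts utilizing a two-way ANOVA". Time is handled as a repeated factor within infants, and the Geisser-Greenhouse adjustment is specified. A Sidak test then assesses "differences between cohorts at each of the 10 time points assessed". No covariate is named, and the text does not say what *changes* are measured from. The measures "will be measured at 10 distinct time points (Table 1) during serial casting and following in-office TAL"; that Table 1 cannot be identified in the text supplied.

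Section 6.0, Tenotomy, sets out the day in order. The first entry is: "Baseline: FLACC and pulse ox data will be recorded as baby is positioned on treatment table". The next is: "Application of randomized topical cream (either L.M.X.4 or placebo cream) for 30 minutes timed". Three later readings are also labelled baselines, all after the cream; the first of them reads: "Baseline #2: FLACC and pulse ox data will be recorded 30 minutes after cream application". Between the injection and the tenotomy: "Following J-Tip injection there will be a 3-minute break, baby will be calmed during this time". At incision: "Peak FLACC scale and Pulse Ox data will be recorded within 5 seconds of poke of scalpel".

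**The concern.** The pre-cream reading is the one tenotomy-day value that randomised treatment cannot have affected. A value of that kind is normally used as a covariate, so that differences between infants in reactivity at the start do not add noise to the comparison of arms. Here it has no such role. If the ten time points are the tenotomy-day readings, it is instead tested as one of ten outcomes and takes a share of the Sidak correction.

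The repeated-measures structure does not make up for this in the follow-up tests. A contrast of the two arms at a single time point compares different infants. Each infant's own earlier reading enters the arm-by-time interaction, but not that contrast.

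What is at stake is the precision of the comparison closest to Aim 1, pain at incision, using data the trial already collects. The plan names no primary time point; incision is used below for that reason only.

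**Working it through.** **Which readings are the ten?** The readings listed under Tenotomy are: Baseline, cream application, Baseline #2, cream removal, Baseline #3, J-Tip, Baseline #4, incision, start of casting, end of casting. That is exactly ten, and the first precedes the cream. The count supports reading the ten time points as the tenotomy day. The reference to serial casting in section 10.0 keeps the question open.

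**Inputs.** From section 10.0, Power Analysis: difference 2.0 points, SD 4.13 (the maximum SD in the first 39 patients), alpha 0.05, 47 per group; earlier SD 3 with difference 2.5. Assumed: two-sided testing, SD 4.13 applying at incision, and rho (correlation of the pre-cream Baseline with the later score) of 0.1, 0.2, 0.4 and 0.6.

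**The plan's own figures.** By a two-sample t test with 80% power, 2.5 points and SD 3 need 24 per group, as stated. With 2.0 points and SD 4.13 the requirement is 68, not the stated 47. That is a separate matter, and it is why the starting power below is 64%. Only the differences between rows belong to this point.

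**Unadjusted.** Standard error = 4.13 × √(2/47) = 0.852. Noncentrality = 2.0/0.852 = 2.35 on 92 degrees of freedom. Power is 64.2%, and the 95% CI half-width is 1.986 × 0.852 = 1.69.

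**Adjusted.** Residual SD = 4.13 × √(1 − rho²), with one degree of freedom removed. For example, at rho 0.4: 4.13 × √0.84 = 3.78, standard error 0.781, power 71.7%.

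| rho | Variance factor | Residual SD | Power, SD 4.13 | Half-width | Power, SD 3 |
|---|---|---|---|---|---|
| none | 1.00 | 4.13 | 64.2% | 1.69 | 89.2% |
| 0.1 | 0.99 | 4.11 | 64.6% | 1.68 | 89.5% |
| 0.2 | 0.96 | 4.05 | 65.9% | 1.66 | 90.4% |
| 0.4 | 0.84 | 3.78 | 71.7% | 1.55 | 93.7% |
| 0.6 | 0.64 | 3.30 | 82.7% | 1.35 | 97.9% |

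At SD 4.13 the gain is 0.4 / 1.7 / 7.5 / 18.5 percentage points.

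**At the Sidak level (SD 4.13).** Ten tests: alpha = 1 − 0.95^(1/10) = 0.00512, unadjusted power 30.8%. Nine tests: alpha = 1 − 0.95^(1/9) = 0.00568, unadjusted power 32.0%; with the covariate, 32.4 / 33.7 / 39.8 / 54.3%. These figures treat each comparison as a separate t test, which approximates the ANOVA post-test.

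**If *changes* meant score minus pre-cream Baseline.** Variance = SD₁² + SD₀² − 2·rho·SD₁·SD₀, where SD₁ = 4.13 at incision and SD₀ is the Baseline SD. SD₀ is not in the documents, so a range is shown (47 per group, two-sided 0.05):

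| Assumed Baseline SD | rho 0.1 | 0.2 | 0.4 | 0.6 |
|---|---|---|---|---|
| 4.13 | 41% | 45% | 56% | 74% |
| 2 | 59% | 62% | 71% | 82% |
| 1 | 64% | 66% | 70% | 76% |

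The meaning of *changes* can therefore matter a good deal or hardly at all, depending on a Baseline SD that the plan does not give.

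**The case against.** The strongest reply is that nothing here is an error. A repeated-measures ANOVA without a covariate is a legitimate analysis of a randomised trial, and the gain from adjustment may be trivial. Between the pre-cream Baseline and incision come cream application and removal, an injection, a calming break, and coping measures used at staff or family discretion (section 6.0, Standardizing the Environment). A reading taken before all of that may predict the incision peak poorly. At rho 0.1 to 0.2 the gain is under two percentage points of power, and nothing in the documents supports rho of 0.6. All of this stands, and it is why the priority is modest.

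It is also fair that *changes* compared by an ANOVA with matched time measures most naturally means change over time by arm. That needs no single subtraction reference and already uses each infant's own readings. The loss then concerns the per-time-point tests only. Table 1 might also settle the time points or a reference, so its absence from the supplied text cannot be held against the plan.

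A reader might infer three stronger things that the documents do not support:

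- **That the planned comparison is biased or invalid.** Allocation is randomised, so leaving out a baseline covariate costs precision, not validity.
- **That the plan subtracts a post-treatment baseline.** Baselines #2–#4 do follow the randomised cream, but nowhere does the plan say they are subtracted or adjusted for.
- **That the missing covariate explains the 64% power.** That figure comes from pairing 47 per group with 2.0 points and SD 4.13. At that size, adjustment alone would reach 80% only if rho were about 0.56.

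**Conclusion.** The point holds as one of efficiency. The between-arm comparison at each time point names no baseline covariate, although a pre-treatment value of the same measure is collected on the day, and within-infant matching does not supply the adjustment for a contrast at a single time point. Variance is multiplied by 1 − rho², a reduction of 1 / 4 / 16 / 36% at rho 0.1 / 0.2 / 0.4 / 0.6. In the incision example the power gain runs from 0.4 to 18.5 percentage points, and the lower end is quite plausible.

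The size rests on assumed rho, on SD 4.13 applying at incision, and on two-sided testing. The step from ten Sidak tests to nine also depends on the ten time points being the tenotomy-day readings. The meaning of *changes* and the status of Baselines #2–#4 are clarifications, not demonstrated errors. Low-to-moderate priority.

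**What to change.** Keep the arm-by-time ANOVA as planned, and add to section 10.0 wording such as:

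*The between-arm comparison at each post-cream time point on the day of tenotomy will use a linear model (or mixed model) with treatment group and the pre-cream tenotomy-day Baseline of the same measure as covariate, for FLACC, heart rate and oxygen saturation separately.*

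If the ten time points are the tenotomy-day readings, do not test the pre-cream Baseline as an outcome; nine Sidak tests remain.

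As a clarification, state what *changes* means, and that Baselines #2–#4, being taken after the randomised cream, are not used as the reference. They may stay as outcome time points.

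Cost: a short dated amendment and one degree of freedom per comparison, with no new data or visits. It may need software other than the package named in section 10.0. The amendment should precede any unblinded comparison, because FLACC scores from the first 39 patients have already been used to estimate the SD.

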# 9.0 Study Withdrawal/Discontinuation

Participation in this study is voluntary. If at any time a study participant wishes to be withdrawn from the study, they may do so by contacting any of the key study personnel and letting them know they withdraw their consent. The date in which the participant withdraws their consent will be noted in their study file. Any information gathered up to the point of consent withdrawal may still be used for research and reporting.

Enrolled patients will be removed from the study if they are inconsistent with casting follow-up visits, noncompliant with treatment, or if the treating physician recommends TAL in the operating room due to specific patient factors, such as age or size.

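### The plan names a matched ANOVA over ten time points, which classically needs every reading for each infant, and gives no rule for a missing reading.

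*Combined protocol and SAP*

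**What the plan says.** Section 10.0, Data Analysis, states: "FLACC, heart rate, and oxygen saturation will be measured at 10 distinct time points (Table 1"). It continues that "Changes in FLACC score, heart rate, and oxygen saturation will be compared between treatment and control cohorts" by a "two-way ANOVA with a Geisser-Greenhouse correction for matched time measures". For the individual time points, "A Sidak's multiple comparisons test will be utilized to assess differences between cohorts at each of the 10 time points assessed". The software is named: "Statistical analysis will be conducted utilizing GraphPad Prism 8.3.0".

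On the day of the procedure (section 6.0, Tenotomy), FLACC and pulse oximetry are recorded together at a series of events. At the incision, for example, "Peak FLACC scale and Pulse Ox data will be recorded within 5 seconds of poke of scalpel".

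Neither section 10.0 nor any other section states a rule for a missing reading. There is no complete-case rule, imputation, mixed model or defined analysis population. The nearest statement is in section 9.0: "Any information gathered up to the point of consent withdrawal may still be used for research and reporting". That covers an infant whose parents withdraw consent, not a gap in the readings of an infant who stays in the study.

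**The concern.** A classical repeated-measures ANOVA with time as a matched factor works on a complete infant-by-time table. A blank cell means that the infant is left out, the analysis does not run, or something else is substituted. The plan does not choose among these, so the analysed population could be settled by software behaviour or by a decision made after the data are seen.

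Single gaps are foreseeable. Each infant contributes ten readings of each outcome, and some must be captured within 5 seconds of an event. That the tenotomy readings all fall on one day limits dropout but does not prevent an isolated missed value.

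If the analysis is run on complete cases, an infant whose incision FLACC was properly recorded drops out of the FLACC analysis because, say, the score at cream removal was missed. The reading closest to the trial's question would be discarded for want of a less important one. The sample size gives no stated cushion: Power Analysis adds 20% for loss to the original 24 per group and states no allowance with the 47.

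**Working it through.** **Inputs from the documents.** Ten time points and the ANOVA (Data Analysis); difference 2.0 FLACC points, SD 4.13, alpha 0.05, 47 per group (Power Analysis, interim calculation). Sidedness is not stated; two-sided is used here.

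**Assumed input.** The share q of readings lost. The documents give no figure, so q = 1%, 2% and 5% are shown.

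**Does the method need complete rows?** As a check, a repeated-measures ANOVA was run in Python (statsmodels AnovaRM) on simulated data for 20 subjects at ten times with one value deleted. It stopped with an unbalanced-data error. This illustrates the requirement; it says nothing about how Prism 8.3.0 behaves.

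**The plan's own figures.** For a two-sample t-test with n per group, the noncentrality is (difference/SD) × √(n/2), with 2n − 2 degrees of freedom.
- Original calculation: 2.5/3 = 0.83 gives 23.6, so 24 per group. This reproduces.
- Interim calculation: 2.0/4.13 = 0.484. With n = 47 the noncentrality is 0.484 × √23.5 = 2.35 and power is 0.64, not 0.80; 80% power needs 68 per group. That mismatch is a separate matter. Here 0.64 is simply the starting point.

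**Effect of lost readings under complete-case analysis.** Two extremes are shown.
- Independent loss: the share of complete infants is (1 − q)^10.
- Loss fully clustered within infants (those with any gap lose everything): the share is 1 − q.

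| q | Independent: share complete | n per group | Power | Clustered: n per group | Power |
|---|---|---|---|---|---|
| 0 | 1 | 47 | 0.64 | 47 | 0.64 |
| 1% | 0.99^10 = 0.904 | 42.5 | 0.60 | 46.5 | 0.64 |
| 2% | 0.98^10 = 0.817 | 38.4 | 0.55 | 46.1 | 0.63 |
| 5% | 0.95^10 = 0.599 | 28.1 | 0.43 | 44.7 | 0.62 |

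To keep 47 complete infants per group under independent loss, 47/0.904, 47/0.817 and 47/0.599 give 52, 58 and 79 randomised per group. Under full clustering, 47/0.99, 47/0.98 and 47/0.95 give 48, 48 and 50.

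**What using all readings recovers.** Under either pattern, a share 1 − q of infants still has an incision reading. A contrast at the incision that uses every available reading therefore rests on about 47(1 − q) infants per group, the clustered column, even if losses are independent. The gap between the two power columns is roughly what complete-case analysis would give away.

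**The case against.** The strongest reply is that the plan never says it will delete infants. That is correct. A reader might infer from the choice of ANOVA that only infants with every reading are analysed, but the documents contain no such rule and do not say how Prism 8.3.0 treats a gap. What the documents support is narrower: a complete-data method is named and nothing is said about gaps.

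A second tempting inference is that the surviving infants would be the calmer ones, so that the pain comparison is biased. The mechanism is movement artefact in pulse oximetry, which bears on heart rate and saturation. FLACC is scored by observation with a trained research assistant present, and a lost oximetry value leaves the FLACC row intact. Nothing in the documents suggests that FLACC goes missing in distressed infants. Even for oximetry the evidence is indirect. The statement that the "patient will wear pulse ox on hand, with mitten covering tool if needed" belongs to the weekly casting visits and includes a precaution; the Tenotomy section does not give the probe site.

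Third, the exposure to missed windows can be overstated. The Tenotomy section lists ten readings, but only four carry a 5-second limit: cream application, cream removal, injection and incision. The other six are baselines or the start and end of casting. Data Analysis also mentions serial casting, so it is not certain that these are the ten meant; if the ten span several visits, gaps become more likely.

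Fourth, the loss rates are assumed, and independence is the unfavourable extreme. With full clustering the power loss is about 2 points or less. The calculation is also a plain two-group t-test on FLACC, not the planned ANOVA with Sidak comparisons. It uses 47 per group, whereas section 5.0 speaks of 94 patients at each site and section 12.0 of 48 in total. With 94 per group across two sites, the same independent losses would take power from 91% to 88%, 85% or 72%.

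These points limit the size and reach of the problem. They do not supply the missing rule.

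**Conclusion.** The point stands in this limited form: the plan names an analysis that classically requires all ten readings per infant and gives no rule for a missing one, while a method that keeps partial rows is available at little cost.

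If complete-case analysis were applied, assumed reading losses of 1%, 2% or 5% would lower FLACC power from 0.64 by about 0 to 4, 1 to 9 or 2 to 21 percentage points. The range within each rate runs from full clustering to independence. These figures are illustrations that rest on the assumed rates, 47 per group, SD 4.13 and a two-sided t-test.

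The documents do not support saying that the plan discards incomplete infants, or that the FLACC comparison is tilted toward calm infants. For heart rate and saturation such a tilt is plausible but remains an inference.

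**What to change.** In section 10.0, Data Analysis, replace the ANOVA sentence with wording along these lines: *FLACC, heart rate and oxygen saturation will each be analysed with a mixed-effects repeated-measures model with treatment, time and treatment-by-time as fixed effects and a within-infant covariance structure, fitted to all available readings. Between-cohort differences at each of the ten time points, including the incision, will be estimated from this model with Sidak adjustment. The number and percentage of readings available will be reported by outcome, time point and arm.*

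This keeps the planned comparisons and does not introduce a new primary time point. The covariance structure should be named in advance, and the team should confirm that the stated software fits the model or name software that does.

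The cost is SAP wording and slightly more analysis work, with no new data. The limitation is that the model does not remove bias if loss depends on distress that was not observed. The completeness table is there to show whether that is a live concern, chiefly for heart rate and saturation.
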